1. INTRODUCTION

This statistical analysis plan (SAP) provides the detailed methodology for summary and statistical analyses of the data collected in Study INDV-2000-105 and is based on the original protocol dated 15May2023. This SAP supersedes the statistical considerations stated in the protocol; any differences are identified in Section 6.2 (Appendix 2) of this document. However, major modifications of the primary endpoint definition or its analysis will also be reflected in a protocol amendment. Post hoc or unplanned analyses not specified in the SAP will be documented in the clinical study report (CSR).

Note: INDV-2000 is the current name for the IDV184001 drug compound, and IDV184001 is the active moiety of IDV184001AN.

VERSION HISTORY

SAP Version	SAP Finalization Date	Associated Protocol Version	Protocol Approval Date	Change	Rationale
1.0	15Nov2023	Original	15May2023	Not Applicable	Original version

 Table 1
 SAP Version History Summary

		TRA PK parameters in urine, feces, and urine+feces: Ae _{t1-2} , CumAe, and CL _r (urine only) [Time Frame: Pre-dose to 168 hours post-dose, collection time can be extended].	РК	Numeric descriptive
		Unlabeled IDV184001 and M12 PK parameters in plasma: AUC _{last} , AUC _{0-∞} , AUC _{extrap(%)} , C _{max} , T _{max} , λ_z , T _{1/2} , as data permits [Time Frame: Pre-dose to 168 hours post-dose].	РК	Numeric descriptive (median and range only for T_{max})
		Ratio of unlabeled IDV184001 and M12 in plasma to plasma TRA for AUC _{last} and C_{max} , where appropriate [Time Frame: Pre-dose to 168 hours post-dose].	РК	Numeric descriptive

Objective Clinical Category	Statistical Category	Variable/Endpoint	Pop- ulation	Population-Level Summary
PK (continued)	Primary (continued)	Identification of parent and metabolites in plasma, urine, and feces.		Descriptive
		% of AUC of each metabolite in plasma, % of dose of each metabolite in urine, % of dose of each metabolite in feces [Time Frame: Pre-dose to 168 hours post-dose, collection time can be extended]	PK	Numeric descriptive
		The ratio of TRA concentration equivalents in whole blood relative to plasma at each time matched determination of TRA in whole blood and plasma [Time Frame: Pre-dose to 168 hours post-dose, collection time can be extended].	PK	Numeric descriptive
Secondary Objective				
To assess the safety	/ and tolerabilit	ty of a single oral dose of [¹⁴ C]-IDV184001AN as determined by ac	dverse ever	nt (AE) reporting.
Safety	Secondary	Incidence, seriousness, severity, and relatedness of treatment- emergent AEs (TEAEs).	Safety	Categorical descriptive
Tertiary/Exploratory	Objective			

		Estimand		
Objective	Statistical		Pop-	
Clinical Category	Category	Variable/Endpoint	ulation	Population-Level Summary

1.2. Study Design

This is a Phase I open-label, single-center, single-dose study in healthy adult male participants to characterize the absorption, metabolism, excretion, and mass balance of $[^{14}C]$ -IDV184001.

The study schematic is depicted in Figure 1.

Figure 1. Study Schematic

a. Day 1 to 8 : Blood sample collection for TRA (whole blood and plasma), unlabeled INDV-2000 and M12 PK (plasma), and metabolite profiling (plasma) ; urine and fecal sample collection for TRA and metabolite profiling.

b. Participants may be discharged from the study site following the 168-hour post-dose blood draw and/or study procedures on Day 8, if at least one discharge criterion is met . If neither discharge criteria is met by 168 hours post-dose (i.e., Day 8), participants will remain confined at the CRU until at least one discharge criterion is met or a maximum stay of 21 days post-dose is reached (i.e., Day 22).

c. Participants who terminate the study early will be asked to return to the study site 7±2 days after the last dose for follow-up procedures, and to determine if any AE has occurred since the last study visit.

Abbreviations: AE=adverse events; ET= Early termination; PK=pharmacokinetics; TRA= total radioactivity.

Key features of the study design are described below.

- Approximately 7 healthy adult males will be enrolled to ensure at least 6 participants complete the study.
- On Day 1, participants will receive a single oral dose of 200 mg (~100 μCi) [¹⁴C]-IDV184001AN.
- Blood (for plasma and whole blood), urine, and fecal samples will be collected pre-dose and for at least 168 hours post-dose (ie, Day 8) to measure TRA (all sample matrices), and for metabolite identification, profiling and quantitation (plasma, urine, and feces), as appropriate. Blood samples for plasma concentrations of unlabeled IDV184001 and M12 will also be collected for at least 168 hours post-dose.
- Participants may be discharged from the study site following the 168-hour post-dose blood draw and/or study procedures on Day 8, if at least one discharge criterion is met (refer to Protocol Section 4.1.1 If the study study post-dose (ie, Day 8), participants will remain confined at the study site until at least one discharge criterion is met or a maximum stay of 21 days post-dose is reached (ie, Day 22), whichever is first.

- For participants who remain confined past Day 8, collection of urine and fecal samples for TRA determination and metabolite identification, profiling and quantitation will continue in 24-hour intervals and collection of blood for TRA determination (whole blood and plasma) and metabolite identification, profiling and quantitation (plasma) will continue in 72-hour intervals.
- The total planned study duration for each participant will be up to 7 weeks. This includes a screening period of up to 4 weeks and a treatment period of at least 1 week (Days 1 to 8) up to a maximum of 3 weeks (Days 1 to 22) until at least one discharge criterion is met.

2. STATISTICAL HYPOTHESES

There are no formal statistical hypotheses for this study.

2.1. Multiplicity Adjustment

There will be no formal statistical inference in this study; therefore, there will be no multiplicity adjustment.

3. SAMPLE SIZE DETERMINATION

Approximately 7 participants will be enrolled to ensure 6 participants complete the study. The sample size was selected without statistical considerations. It has been determined adequate to meet the study objectives and is in accordance with the Food and Drug Administration guidance.^{1, 2} This sample size is limited based on clinical considerations for this type of study and in order to limit exposure to radioactivity.

4. POPULATIONS FOR ANALYSIS

Data for all participants will be assessed to determine if they meet the criteria for inclusion in each analysis population shown in Table 3 prior to releasing the database. Classifications will be documented per standard operating procedures.

Population	Description
Screened	Participants who signed informed consent.
Safety Analysis Set	Participants who received the study drug.
PK Analysis Set	Participants who received the study drug and had an adequate number of PK samples collected to derive any ADME (absorption, distribution, metabolism and excretion) parameter and have no protocol deviations that would significantly alter disposition of study drug.

Table 3	Analysis Populations
---------	----------------------

5. STATISTICAL ANALYSES

5.1. General Considerations

5.1.1. Timing of Analyses

Safety data will be reviewed on an ongoing basis. There will be a production run of tables, figures, and listings (TFLs) after the database has been locked following the study-level EOS.

5.1.2. Programming Environment

SAS[®] version 9.4 or higher (SAS Institute, Cary, North Carolina) will be used for statistical analyses and for the production of Study Data Tabulation Model (SDTM) and Analysis Data Model (ADaM) data sets as well as TFLs.

5.1.3. Reporting Conventions

Data will be summarized by visit, where applicable. TFL tables of contents, mock-ups, and specifications are provided in a separate document from the SAP. The following reporting conventions will be followed:

- Tables and figures will present summaries/analyses by study visit and time point, as appropriate.
- Table column headers and figure legends will include sample size ("N = xx"), where applicable. Sample sizes reported as part of descriptive statistics ("n") will be the number of non-missing observations.
- Listings will generally include unique subject identifier; study visit/time point; assessment or collection date/time; parameter; and observed value.

5.1.4. General Analysis Conventions

Categorical variables will be summarized using frequencies and percentages. Percentages will be reported to one decimal place.

Continuous variables will be summarized using descriptive statistics (e.g., n, mean, standard deviation (SD), distribution percentiles, range). The number of decimal places for minimums and maximums will be the same as the original data. The number of decimal places for means, medians, and interquartile ranges will be the same as the original data plus one, and the number of decimal places for measures of variance will be the same as the source data plus two. See Appendix 6.4.1 (Appendix 4) for summary statistics and precision specifications for PK data.

Data with qualifiers (e.g., "<") will be listed with but summarized without the qualifier.

5.1.5. Definitions

Study Drug: IDV184001AN + $[^{14}C]$ -IDV184001AN

Screening Period: Informed consent to Day -1 Clinic Check-In.

Day -1 Clinic Check-In: clinic check-in to date/time of dosing on Day 1.

Study Day 1: day of study drug dosing.

Study day:

- Study day = date of assessment date of Study Day 1 + 1, for assessments on or after Study Day 1
- Study day = date of assessment date of Study Day 1, for assessments before Study Day 1

Duration:

- Duration in days = end date start date + 1
- Duration in minutes = end time start time

Baseline observation: for a given parameter for a given subject, the last observed value, including unscheduled and repeated assessments, before study drug dosing.

EOS, Subject-Level: Early termination or completion of discharge criteria or completion of a 21-day clinic stay post-dose (ie, Study Day 22).

EOS, Study-Level: Study completion for the last subject.

5.2. Study Conduct and Participant Disposition

Subject disposition summaries will include the number of subjects screened and the number and percentage of subjects who were screen failures, who were otherwise not enrolled, who were enrolled, who were in each analysis population, and who completed the study. For percentages, the number of subjects screened will be the denominator for screen failures, for subjects not otherwise enrolled, and for subjects who were enrolled, and the number of subjects enrolled will be the denominator for the Safety Analysis Set, the PK Analysis Set and for subjects completing the study.

Reason for study discontinuation will also be summarized by number and percentage of subjects for each reason reported; for the percentage, the number of subjects who discontinued will be the denominator.

Reason for screen failure and other non-enrollment will be summarized in a separate table by number and percentage of subjects for each reason reported; the denominator will be the number of non-enrolled subjects.

5.3. Primary Endpoints Analysis

5.3.1. Definition of Endpoints

The primary endpoints are itemized in Table 2.

5.3.2. Main Analytical Approach

Estimand strategy: Principal stratum.

Analysis set: PK (see Table 3).

Analysis methodology:

For TRA recovery and the percentage of the radioactive dose excreted in the urine, feces, and in both excreta combined (mass balance), based on urine sample weights, fecal homogenate weights, IDV184001-concentration equivalents of TRA in urine and fecal homogenate samples collected at each interval will be used to derive the TRA recovery parameters for each subject using standard non-compartmental methods (see Appendix 6.4.2.2).

For PK analysis, standard non-compartmental methods based on actual sampling times will be used to derive parameters for each subject (see Appendix 6.4.2.1).

Intercurrent events and missing data: Subjects with intercurrent events may be excluded from the PK Analysis Set, to be decided by the sponsor on a case-by-case basis. See Section 6.6.1 (Appendix 6) for details on handling of missing data.

5.4. Secondary Endpoints Analysis

5.4.1. Definition of Endpoints

The secondary endpoints are incidence, seriousness, severity, and relatedness of TEAEs.

5.4.2. Main Analytical Approach

Estimand strategy: Treatment policy.

Analysis set: Safety (see Table 3).

Analysis methodology: Descriptive only.

Intercurrent events and missing data: AEs will be reported regardless of the occurrence of an intercurrent event. See Section 6.6.2 (Appendix 6) for handling of missing AE information.

See Section 5.5.2 for details on AE summaries and listings.

5.5. Tertiary/Exploratory Endpoints Analysis

5.5.1. Definition of Endpoints

5.5.2. Main Analytical Approach

5.6. Other Safety Analyses

5.6.1. Study Drug Exposure

Details of study drug exposure will be listed and summarized. Exposure data will be presented with the same precision as original data in listings, and will be rounded to 2 or 3 decimal places for summarization, depending on the data.

5.6.2. Adverse Events

A TEAE starts at or after study drug dosing. AEs will be coded to a System Organ Class (SOC) and Preferred Term (PT) using Medical Dictionary for Regulatory Activities (MedDRA). Additional details of the coding process, including the current version of the dictionary, are described in the Data Management Plan.

All AEs will be listed for individual subjects. Listings will include SOC, PT, and reported term; onset date and time, end date, and duration; treatment-emergence, severity, toxicity grade, seriousness and seriousness criteria; relationship to study drug; whether concomitant treatment was given; outcome; and whether the AE resulted in study discontinuation. Duration (days) is calculated as the AE end date – the AE onset date +1; for ongoing AEs, the date of end of study participation will be used as the end date. Duration will be missing if either the start or end date is partially or completely missing. TESAEs, TEAEs leading to study discontinuation, and fatal TEAEs will be listed separately.

The incidence and number of all TEAEs, TESAEs, study drug-related TEAEs and study drug-related TESAEs, severe TEAEs, TEAEs with grade 3 or higher toxicity grade, TEAEs leading to study discontinuation, and fatal TEAEs will be presented in an overall summary table.

TEAEs, TESAEs, study drug-related TEAEs and study drug-related TESAEs will be summarized by MedDRA SOC and PT, each in descending order of frequency among all subjects (then alphabetically in case of ties). TEAEs will also be summarized by maximum severity and by maximum toxicity within SOC and PT. If an AE is reported more than once by a subject within a SOC and/or PT, the maximum reported level of severity/toxicity will be used at each level of summation in the severity/toxicity summary tables. Incidence and number of TEAEs will also be summarized by PT only (ie, not SOC), sorted by descending frequency among all subjects.

Non-TEAEs are defined as AEs that started before study drug dosing. Non-TEAEs will be summarized for the Safety Analysis Set.

See Section 6.6.2 (Appendix 6) for details on handling of missing AE information.

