4.4 End of Study Definition

The end of the study is defined as the discharge or early termination date.

A participant is considered to have completed the study if the participant completed dosing, did not discontinue or terminate the study early, and has completed the discharge criteria (Section 4.1.1).

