7.2 Participant Discontinuation/Withdrawal From the Study

- A participant may withdraw from the study at any time at the participant's own request for any reason (with or without providing any reason).
- A participant may be withdrawn at any time at the discretion of the Investigator for safety, behavioural or compliance reasons.
- At the time of discontinuing from the study, if possible, discharge assessments should be conducted, as shown in the SoE (Section 1.3).
- Participants who terminate the study early will be asked to return to the study site 7±2 days after dosing for follow-up procedures, and to determine if any AE has occurred since the last study visit, as shown in the SoE (Section 1.3).
- The participant will be permanently discontinued both from the study drug and from the study at that time.
- The participant will be encouraged to stay up to 24 hours post-dose to complete discharge assessments.
- If the participant withdraws consent for disclosure of future information, Indivior may retain and continue to use any data collected before such a withdrawal of consent.
- If a participant withdraws from the study, the participant may request destruction of any samples taken and not tested, and the Investigator must document this in the site study records.

Should any participant withdraw or be withdrawn from the study, they will be cautioned against activities requiring mental alertness, judgment and physical coordination such as driving, operating machinery, or power equipment for a period of 24 hours post-dose.

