8.4.1 Time Period and Frequency for Collecting AE and SAE Information

All AEs and SAEs will be collected from ICF signature until discharge on Day 8 (up to Day 22). Any ongoing AEs at the time of discharge will be appropriately followed-up until resolution or 14 days (±2 days) after discharge or early termination. Any ongoing SAEs will be followed-up until resolution or lost to follow-up.

All SAEs will be recorded and reported to Indivior or designee immediately and under no circumstance should this exceed 24 hours from first becoming aware of the event, as indicated in Section 8.4.3. The Investigator will submit any updated SAE data to Indivior within 24 hours of it being available.

Investigators are not obligated to actively seek AEs or SAEs after conclusion of the study participation. However, if the Investigator learns of any SAE, including a death, at any time after a participant has been discharged from the study, and the Investigator considers the event to be reasonably related to the study drug or study participation, the Investigator must promptly notify Indivior.

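### In the AE listings, the SAP cuts the duration of an unresolved adverse event at the end of study participation, about 14 days before the protocol's own follow-up of that event ends

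*SAP*

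**What the plan says.** SAP 5.6.2 defines the calculation: "Duration (days) is calculated as the AE end date – the AE onset date +1". For an event without an end date it adds that "for ongoing AEs, the date of end of study participation will be used as the end date". The only safeguard concerns incomplete dates: "Duration will be missing if either the start or end date is partially or completely missing".

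The SAP does not define *end of study participation*. The nearest definitions are in Protocol 4.4, "The end of the study is defined as the discharge or early termination date", and in SAP 5.1.5, where subject-level end of study is "Early termination or completion of discharge criteria or completion of a 21-day clinic stay post-dose".

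The protocol keeps observing events after that date. Section 8.4.1 says: "Any ongoing AEs at the time of discharge will be appropriately followed-up until resolution or 14 days (±2 days) after discharge or early termination". The same section follows serious events until they resolve or contact is lost, with no 14-day limit. Section 7.2 asks early terminators to come back 7±2 days after dosing, partly "to determine if any AE has occurred since the last study visit".

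**The concern.** The imputed end date falls before the protocol stops watching the event. Among events still open at discharge, those that resolve in follow-up have a real end date, and those that do not resolve are assigned the earlier discharge date. The less favourable course then gets the smaller number, and the error always runs towards making an unresolved event look brief.

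The early terminator raises a second difficulty. The return visit exists to find events that began after the participant left. If participation ends on leaving, such an event, still open at the visit, is given an end date before its onset.

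What is at stake is the accuracy of the subject-level safety listings. With about 7 participants dosed and a purely descriptive safety analysis, those listings are where a reader sees how a single event developed.

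**Working it through.** The documents give no AE duration figure to reproduce, so the check applies the SAP's formula to the protocol's timings.

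**Inputs**
- Duration = end day − onset day + 1 (SAP 5.6.2).
- End day for an ongoing event = end of participation, read as discharge or early termination (Protocol 4.4, SAP 5.1.5).
- Discharge from Day 8 to Day 22; follow-up of open events for 14±2 days after discharge or early termination (Protocol 8.4.1).
- Return visit for early terminators 7±2 days after dosing on Day 1, which is Day 6 to Day 10 (Protocol 7.2).
- Onset, resolution and termination days below are illustrative assumptions.

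**Completer, discharge Day 8, onset Day 7**

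| Course | Calculation | Days |
|---|---|---|
| Resolves in follow-up on Day 18 | 18 − 7 + 1 | 12 |
| Unresolved on Day 22, as listed under the SAP | 8 − 7 + 1 | 2 |
| Unresolved on Day 22, minimum actually known | 22 − 7 + 1 | 16 |

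**Size in general.** For discharge day d, onset day o and follow-up of k days, the known minimum less the listed value is (d + k − o + 1) − (d − o + 1) = k. The understatement is therefore 14 days (12 to 16 with the ±2 window), whatever the onset or discharge day. For an unresolved serious event k can exceed 16.

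**Where the ordering does not invert.** With discharge on Day 8 and onset on Day 2, an event resolved on Day 3 is listed as 3 − 2 + 1 = 2 days, and one that never resolves as 8 − 2 + 1 = 7 days. The inversion is confined to comparison with events of the same onset that resolve during post-discharge follow-up.

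**Early terminator, if participation ends at termination.** With termination on Day 2, onset on Day 5, and the event still open at the return visit, the listed duration is 2 − 5 + 1 = −2 days. Onset one day after termination gives 0; onset two or more days after gives a negative value. The incomplete-date safeguard does not catch this, because both dates are complete.

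**Release lag.** Protocol 4.1 allows release about a day after a discharge criterion is met. If the end date is the day the criterion is met (Day 8), an event starting on Day 9 before release and still ongoing gets 8 − 9 + 1 = 0 days.

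**The case against.** The strongest reply is that very little depends on this column. The secondary endpoints are incidence, seriousness, severity and relatedness of TEAEs (SAP 5.4.1), and none of the AE tables in SAP 5.6.2 uses duration. The listing also shows outcome, so a reader can tell that an event did not resolve. The mock-ups are in a separate document (SAP 5.1.3) and may carry an ongoing flag. All of this stands and limits the consequence, but it does not make the number correct.

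A reader might infer that follow-up data are discarded, or that an unresolved event is presented as having ended. The documents do not support either. True resolution dates remain in use, outcome is listed, and nothing in the SAP removes information gathered after discharge. For unresolved events, one derived value stops too early.

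A reader might also infer that unresolved events are in general listed as shorter than resolved ones. That is not so, as the Day 2 example shows.

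The negative duration is open to challenge as well. Protocol 8.4.1 says investigators need not actively seek events once study participation has concluded, yet the return visit is held to seek them. That suggests participation could include the visit, and then no negative value arises for an event found there. Against this, Protocol 7.2 treats a withdrawing participant as discontinued from the study at the time of withdrawal. The text does not settle the matter, so the negative value can only be stated conditionally. It also needs an uncommon case: an early terminator (Protocol 9.5 allows for at most 1 of 7), a late onset, and no resolution by the visit.

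**Conclusion.** The point holds as an error in a listing rule. On the only definitions the documents supply, an adverse event unresolved at the end of follow-up is listed about 14 days too short (12 to 16), and by more for an unresolved serious event followed longer. An event of the same onset that resolves during follow-up is listed at its true length, so the listing can reverse the order of the two.

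This rests on two assumptions. The first is that *end of study participation* means discharge or early termination. The second is that resolution dates after discharge reach the CRF, as Protocol 8.4.3.2 implies. If they did not, every event open at discharge would be cut there; the reversal would disappear but the understatement would remain.

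A negative duration is possible only if the undefined term means the early termination date and the onset is at least two days later. The effect is confined to the duration column of the AE listings. It would be wrong to conclude that the secondary endpoint or any planned AE summary is biased: TEAE incidence, seriousness, severity and relatedness do not depend on it.

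**What to change.** In SAP 5.6.2, replace the imputation with a rule along these lines: *No end date is imputed for an AE unresolved at last follow-up. It is listed as ongoing, with a minimum duration (≥ x days) calculated to the last recorded AE follow-up date, including follow-up after discharge and the early-termination return visit.* In the completer example the entry becomes ≥ 16 days instead of 2. For the early terminator with onset on Day 5 and a last contact on Day 8, it becomes ≥ 4 days (8 − 5 + 1) instead of −2. If the term *end of study participation* is kept anywhere, define it in SAP 5.1.5 and say whether it includes the return visit.

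The cost is one SAP sentence, a change to the listing format, and confirmation that the CRF captures the follow-up contact date, which the documents do not show. No protocol procedure, endpoint or summary table changes.
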